6.4 STATISTICAL ANALYSIS

All statistical analyses will be performed using Statistical Analysis System (SAS), R, or S-Plus statistical software. No formal multiple comparison adjustments will be employed for safety endpoints or secondary endpoints.

6.4.1 Analysis Variables

The analysis variables consist of baseline variables and safety variables for primary and secondary objective analyses.

6.4.2 Baseline Demographics

Baseline characteristics including demographics and laboratory measurements will be summarized using descriptive statistics.

6.4.3 Safety Analysis

6.5.3.1 Reactogenicity

The number and percentage of participants experiencing each type of reactogenicity sign or symptom will be tabulated by severity. For a given sign or symptom, each participant's reactogenicity will be counted once under the maximum severity for all assessments.

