3. STUDY OBJECTIVES

3.1 PRIMARY OBJECTIVES

- To evaluate the safety and tolerability of the VRC-FLUNPF099-00-VP vaccine, administered as a single dose at 20 mcg IM via needle and syringe on Day 0 to healthy adults.
- To evaluate the safety and tolerability of the VRC-FLUNPF099-00-VP vaccine, administered at 60 mcg IM via needle and syringe to healthy adults by repeat dosing on Day 0 and Week 16 for a total of 2 injections.

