Subjects will be given a “Diary Card” to use as a memory aid, on which they can record temperature and symptoms daily for 7 days after each injection. Subjects will be trained and encouraged to use the secure electronic database but will have the option to complete a paper diary card. When the diary card parameters are recorded directly by the subject in the electronic database, the subject’s electronic record will be the source for these data. When collected on paper, the paper diary card will be the source document. When neither paper nor electronic diary is available from the subject, the study clinician will document the source of reactogenicity information recorded in the study database.

The solicited signs and symptoms on the diary card will include the following parameters: unusually tired/feeling unwell, muscles aches (other than at injection site), headache, chills, nausea, joint pain, and pain/tenderness, redness, swelling, skin lesions at injection site. Subjects will also record the day’s highest measured temperature and measurement of largest diameter for redness and swelling at injection site.

Follow-up on subject well-being will be performed by telephone on the first day following all injections and by clinic visits as shown in the Schedule of Evaluations ([Appendix I](#)).

Events following any study injection that may require clinical evaluation include rash, urticaria, fever of 38.5°C (Grade 2) or higher lasting greater than 24 hours, or significant impairment in the activities of daily living. Additionally, other clinical concerns may prompt a study visit based on the judgment of a study clinician.

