6.2 ENDPOINTS

6.2.1 Primary Endpoints: Safety

Assessment of product safety will include clinical observation and monitoring of hematological and chemical parameters. Reactogenicity will be closely monitored for 7 days after each injection and safety evaluated by clinical visits for 52 weeks following the last vaccine administration and through an influenza season. See Section 4.2 and Appendix I for details and specified time points. The following parameters will be assessed for all study groups:

- Occurrence of solicited local reactogenicity symptoms for 7 days after each injection
- Occurrence of solicited systemic reactogenicity symptoms for 7 days after each injection
- Change from baseline in safety laboratory measures

- Occurrence of AEs of all severities through the 4 week post-injection visit
- Occurrence at any time throughout the study of SAEs or new chronic medical conditions that require ongoing medical management.

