6.3.1 Power Calculations for Safety

The goal of the safety evaluation for this study is to identify safety concerns associated with injections of the investigational vaccine. Primary sample size calculations for safety are expressed in terms of the ability to detect serious adverse experiences. Other sample size calculations for comparing the two vaccination groups on adverse experiences are similar to the calculations for immunogenicity (Section 6.4.3).

The ability of the study to identify SAEs will be expressed in terms of the probability of observing a certain number of SAEs. Useful values are the minimum true rate such that the probability of observing at least one event is at least 90%, and the maximum true rate such that the probability of not observing any event is at least 90%.

For Group 1 (*dose-escalation*) within each group (n=5), there is a 90% chance to observe at least 1 SAE if the true rate is at least 0.369 and over 90% chance to observe no SAE if the true rate is less than 0.021.

For Groups 2A, 2B, 2C, 2D within each group (n=12), there is greater than a 90% chance to observe at least 1 SAE if the true rate is at least 0.175 and over a 90% chance to observe no SAE if the true rate is no more than 0.009.

If Groups 2A, 2B, 2C, 2D are combined (N=48), there is greater than a 90% chance to observe at least 1 SAE if the true rate is at least 0.047 and greater than a 90% chance to observe no SAE if the true rate is no more than 0.002

Probabilities of observing 0 or more than 1 SAE within each group are presented in **Table 6-1** for a range of possible true event rates and different sample sizes. These calculations provide a

complete picture of the sensitivity of this study design to identify potential safety problems with the vaccine.

Table 6-2 gives the upper and lower bounds for 95% exact binomial confidence intervals of the true SAE rate at all possible numbers of events within each group (n=5 and n=12).

For Group 1 (n=5): If none of the 5 participants receiving the vaccines experience SAEs, the 95% exact 2-sided upper confidence bound for the SAE rate is 0.52.

For Groups 2A, 2B, 2C, 2D (n=12): If none of the 12 participants receiving the vaccines experience SAEs, the 95% exact 2-sided upper confidence bound for the SAE rate is 0.265.

Table 6-1: Probability of Events for Different Safety and Immunogenicity Scenarios

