6.5.3.2 Adverse Events

AEs are coded into Medical Dictionary for Regulatory Activities (MedDRA) preferred terms. The number and percentages of participants experiencing each specific AE will be tabulated by severity and relationship to treatment. For the calculations in these tables, each participant's AE will be counted once under the maximum severity or strongest recorded causal relationship to treatment.

A complete listing of AEs for each participant will provide details including severity, relationship to treatment, onset, duration and outcome.

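### As written, the solicited reactogenicity table takes one maximum per participant across both injections, so for Group 2 it cannot give the rate after injection 2, although the primary endpoint is defined after each injection

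*Combined protocol and SAP*

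**What the plan says.** **Endpoint and objective.** Section 6.2.1 lists as primary endpoints "Occurrence of solicited local reactogenicity symptoms for 7 days after each injection" and "Occurrence of solicited systemic reactogenicity symptoms for 7 days after each injection". The second primary objective (Section 3.1) is safety and tolerability of 60 mcg given "by repeat dosing on Day 0 and Week 16 for a total of 2 injections". Table 1 gives Group 1 (n=5, ages 18-40) one 20 mcg injection, and Groups 2A-2D (12 each, 48 in all) two 60 mcg injections.

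**Data collection.** Under Section 4.2.6, participants use a diary card to "record temperature and symptoms daily for 7 days after each injection".

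**Solicited reactions, analysis.** Section 6.5.3.1 (within 6.4.3) tabulates each sign or symptom by severity. Within a symptom, each participant's "reactogenicity will be counted once under the maximum severity for all assessments". No split by injection and no denominator for injection 2 is given.

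**Unsolicited events, analysis.** Section 6.5.3.2 has a similar but not identical rule: each participant's "AE will be counted once under the maximum severity or strongest recorded causal relationship to treatment". It adds a per-participant listing: "A complete listing of AEs for each participant will provide details including severity, relationship to treatment, onset, duration and outcome". No listing is stated for solicited reactions.

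**Group comparison.** Section 6.3.1 refers to sample-size calculations for "comparing the two vaccination groups on adverse experiences". Section 6.4.3 specifies no such test.

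**The concern.** The endpoint is tied to each injection, but the only planned summary of it is a single maximum over the regimen. Two things are at stake.

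- **Separation.** In a first-in-human study with a repeat-dose regimen, whether the second injection is more reactogenic than the first is a basic tolerability question. A merged table cannot answer it, and the plan describes no other summary or listing of solicited reactions that would.
- **Unequal windows.** A Group 2 participant has two 7-day windows in which to become a counted reactor; a Group 1 participant has one. Someone who reads the groups side by side could take that difference for an effect of dose level.

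**Working it through.** **1. The plan's own safety figures reproduce.**

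- Upper 95% bound with no events, 1 - 0.025^(1/n): 0.522 for n=5 and 0.265 for n=12.
- Rate giving a 90% chance of at least one event, 1 - 0.1^(1/n): 0.369 (n=5), 0.175 (n=12), 0.047 (n=48).

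These agree with Section 6.3.1 and are not in dispute.

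**2. Can the injection-2 rate be recovered from the merged table?** Take a hypothetical Group 2 entry of 24/48 for one symptom, with all 48 having received both injections. Each of these patterns produces it:

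| Reactors after injection 1 | Reactors after injection 2 | Merged entry |
|---|---|---|
| 24 | 0 | 24/48 |
| 0 | 24 | 24/48 |
| 24 | the same 24 | 24/48 |

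The injection-2 rate may be 0/48 (exact 95% CI 0 to 0.074) or 24/48 (0.352 to 0.648), or anything between. Likewise, with independent injections, 10% followed by 30% gives 1 - 0.9 × 0.7 = 37%. A constant 20.6% gives the same, since 1 - √0.63 = 0.206.

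**3. How far can two windows differ from one?** Let p be the per-injection rate, equal for every injection in both groups, and r the within-person correlation between injections.

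P(reaction after at least one of two injections) = 2p - [p² + r·p(1-p)] = p + (1-r)·p(1-p)

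Group 1 shows p, so the Group 2 excess is (1-r)·p(1-p). It is zero at r=1 and p(1-p) at r=0.

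The documents give no per-injection rate for this vaccine. Section 1.3.1 reports per-subject figures for another ferritin vaccine: local pain/tenderness 7/47 = 14.9%, any systemic symptom 18/47 = 38.3%, and mild headache 13/47 = 27.7%. They serve here only as assumed values of p.

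| Assumed p | Group 1 | Group 2, r=1 | Group 2, r=0.5 | Group 2, r=0 | Excess (points) |
|---|---|---|---|---|---|
| 14.9% | 14.9% | 14.9% | 21.2% | 27.6% | 0 to 12.7 |
| 27.7% | 27.7% | 27.7% | 37.7% | 47.7% | 0 to 20.0 |
| 38.3% | 38.3% | 38.3% | 50.1% | 61.9% | 0 to 23.6 |

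Among 48 participants at r=0, this is about 13.2 counted reactors instead of 7.1 at p=14.9%, and 29.7 instead of 18.4 at p=38.3%. If injection 2 causes no reactions, the excess is also zero.

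**4. What a table by injection would show.** Each column estimates the rate for that injection, so equal per-injection risk gives equal expected entries in every group.

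**The case against.** **The wording may be read more kindly.** Section 6.5.3.1 is a counting rule, not a table shell, and it does not mention groups either. The assessments it refers to could be the daily entries within one 7-day diary. That reading is possible, but the text does not state it; taken literally, the rule takes one maximum over everything. The ambiguity is itself a reason to add the split.

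**A regimen-level maximum is legitimate.** For the objective of two-injection safety, the proportion with any reaction over the regimen is a valid summary, not a biased one. This stands, and it is why that summary should be kept.

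**No decision rests on the table.** Escalation and continuation reviews use data from two weeks after the third subject's first vaccination (Section 4.3). Self-limited solicited reactogenicity that is not an SAE does not count towards a pause (Section 4.5.1). This stands, and it limits the weight of the point.

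**Stronger readings that the documents do not support.**

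- *That second-injection reactions are missing.* They are counted, but merged with those after injection 1; the diary data remain separable.
- *That the AE table has the same fault in full.* Section 6.5.3.2 does not refer to all assessments, and its listing includes onset, so an AE can be assigned to an injection.
- *That Group 2 is necessarily inflated.* The excess runs from zero. The borrowed rates are per subject, from a trial that included a repeat-dose regimen (Section 1.4), so true per-injection rates there may be lower. The 38.3% figure is a composite, whereas the rule counts each symptom separately.
- *That a false dose signal would be declared.* No test is planned, and Group 1 has five participants (1/5 has an exact 95% CI of 0.005 to 0.716 in Table 6-2). Even at r=0, a two-sided 5% Fisher's exact test of 5 versus 48 would reject with probability 0.2% at p=14.9% and 13.2% at p=38.3%.
- *That participants who miss injection 2 stay in its denominator.* Section 4.4.1 keeps them in follow-up, but no table denominator is stated either way.

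**Conclusion.** The point holds for solicited reactogenicity. Followed as written, Section 6.5.3.1 does not deliver the endpoint of Section 6.2.1: for Group 2 the rate after injection 2 cannot be separated, and it can lie anywhere from zero up to the merged rate.

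The effect on a side-by-side reading with Group 1 is conditional. The ranges of 0 to 12.7 and 0 to 23.6 points rest on equal per-injection risk, non-negative within-person correlation, and assumed rates from another vaccine. That reading is in any case confounded by dose (20 versus 60 mcg) and, in Groups 2B-2D, by age.

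This is a correction to the analysis text with little cost. It does not undermine the design, the stated precision or any stated safety decision. It is best made before the tables are produced, so that in an open-label study the split is not a choice made after seeing the data.

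**What to change.** In Section 6.5.3.1, replace the counting rule with wording such as: *For each group and each injection, each participant is counted once per sign or symptom at the maximum severity recorded in the 7 days after that injection. The denominator is the participants who received that injection. An overall row gives each participant's maximum across all injections received.*

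Three further points:

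- Optionally, split the AE table in Section 6.5.3.2 by post-injection window. This is less pressing because the listing already carries onset.
- Base any descriptive reading of 20 versus 60 mcg on injection 1 only, Group 1 against Group 2A (both ages 18-40), with a note that n=5 makes it imprecise.
- Do not let the overall row for Group 2 stand beside the Group 1 entry without stating the number of injections.

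The cost is a text change and additional table columns. No new data are needed, and no sample-size or precision figure in Section 6.3 changes.

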6.5.3.2 Adverse Events

AEs are coded into Medical Dictionary for Regulatory Activities (MedDRA) preferred terms. The number and percentages of participants experiencing each specific AE will be tabulated by severity and relationship to treatment. For the calculations in these tables, each participant's AE will be counted once under the maximum severity or strongest recorded causal relationship to treatment.

A complete listing of AEs for each participant will provide details including severity, relationship to treatment, onset, duration and outcome.

6.5.3.3 Local Laboratory Values

Boxplots, violin plots, or beeswarm plots of local laboratory values will be generated for baseline values and for values measured during the course of the study. Each plot will show the 1st quartile, the median, and the 3rd quartile. Outliers, or values outside the boxplot, will also be plotted. If appropriate, horizontal lines representing boundaries for abnormal values will be plotted.

6.4.4 Immunogenicity Analysis

The statistical analysis for immunogenicity will employ the intent-to-treat principle whereby all data from enrolled subjects will be analyzed according to the group assignment. However, if during immune assessment on stored samples, a subject is found to have a positive antibody response at baseline, the vaccine immune responses assessment for these subjects will not be included in the final immunogenicity analysis. If needed, a per-protocol analysis will be performed as secondary analysis where subjects will be analyzed according to their actual vaccination scheme if it is different from the assigned or up to the last visit in the study if there are early dropouts. The study is not designed to power the comparison in immune responses between vaccine dosages.

If assay data are qualitative (i.e., positive or negative) then analyses will be performed by tabulating the frequency of positive response for each assay at each time point that an assessment is performed. Binomial response rates will be presented with their corresponding exact 95% confidence interval estimates.

Some immunologic assays have underlying continuous or count-type readout that is often dichotomized into responder/non-responder categories. For these assays, graphical and tabular summaries of the underlying distributions will be made. These summaries may be performed on transformed data (e.g., log transformation) for ease of interpretation.

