3.2 SECONDARY OBJECTIVES

- To evaluate the antibody response to the VRC-FLUNPF099-00-VP vaccine administered as a single dose at 20 mcg IM via needle and syringe at two weeks after injection.
- To evaluate the antibody response to the VRC-FLUNPF099-00-VP vaccine administered as repeat dosing at 60 mcg IM via needle and syringe at two weeks after each injection.

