4.4.1 Discontinuation of Study Injections

A subject will be discontinued from receiving study product for the following reasons:

1. Subject voluntarily withdraws
2. Pregnancy
3. Grade 3 unsolicited AE assessed as possibly, probably or definitely related to study product
4. Grade 4 AE assessed as related to study product
5. Immediate hypersensitivity reaction associated with study product
6. Intercurrent illness that is not expected to resolve prior to the next scheduled study injection
7. Treatment with systemic glucocorticoids (e.g., prednisone or other glucocorticoid) or other immunomodulators (other than nonsteroidal anti-inflammatory drugs [NSAIDs]), with the exception that study injections may continue per investigator discretion if the next dose occurs at least 2 weeks following completion of glucocorticoid treatment

8. The study PI assesses that it is not in the best interest of the subject to continue the vaccination schedule

Group 2 subjects who do not receive the second injection as scheduled are expected to continue follow-up according to the Schedule of Evaluations for Group 1 subjects, except that research sample collections will be discontinued for pregnant women or others in which it is contraindicated.

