6.2.2 Secondary Endpoints: Immunogenicity

The principal immunogenicity endpoints will be assessed by measuring HA-stem specific antibody by pseudo-neutralization assay at:

- Group 1: Baseline (Week 0/Visit 02) and Week 2 (Visit 04) after vaccination, and
- Groups 2A-2D: Baseline (Week 0/Visit 02) and Week 2 (Visit 04) after the first vaccination, and at Week 16 (Visit 07) and Week 18 (Visit 09) after the second vaccination

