³ Study Product Administration: **Group 1** will receive HissF_3928 20 mcg IM at Day 0. Complete post vaccination evaluations (BP, pulse, temperature, respiration and injection site assessment) at **1 hour** or longer after injection.

⁴ Negative pregnancy test results must be confirmed for women of reproductive potential prior to each study injection.

⁵ HLA type blood sample is collected once at any time-point in the study and is shown as a Visit 05 evaluation for convenience; however, if HLA type is already available in the medical record, it does not need to be repeated. HLA type may also be obtained from a frozen sample.

⁶ Visit 03: Two tubes of PBMC collected in EDTA tubes will be sent to Building 40, while the remainder of the blood collected will be sent to VIPVITL.

Visit windows: Schedule Visits 02A - 13 with respect to Day 0 per the following visit windows: Visit 02A (+1 day). Visits 04, 05, 09 (±2 days). Visits 07 (± 7 days). Visit 06 (±14 days). Visits 11, 12 and 13 (± 14 days).

		VRC 321 Schedule of Evaluations: Groups 2A, 2B, 2C, 2D																						
	VRC 500		02	02A	03	04	05	06	07	07A	08	09	10	11	12	13	14							
Visit Number	*01																							
Week of Study	-4 to 0	W0	W1	W2	W4	W12	W16	W17	W17	W17	W17	W18	W20	W28	W40	W52	W68							
Day of Study	-28 to 0	¹ D0	D1	D6	D14	D28	D84	D112	D113	D118	D126	D140	D196	D280	D364	D476								
Clinical																								
*VRC 500 Screening Consent	X																							
VRC 321 AoU; Consent		X																						
² Physical exam for eligibility, height /weight/ vitals at screening; vital signs and targeted exam (as needed) other visits.	X	X	X	X	X	X	X	X	X	X	X	X	X	X	X	X	X							
Medical history targeted to eligibility at screening; then interim medical history	X	X	X	X	X	X	X	X	X	X	X	X	X	X	X	X	X							
³ Study Product Administration: Group 2A-2D		X					X																	
Phone evaluation (clinic visit as needed)			X					X																
Begin diary card		X																						
⁴ Pregnancy test: urine or serum	X	X			X		X					⁸ [X]	X		X	X	X							
⁴ Pregnancy prevention counseling/ Reproductive Information Form	X	X			X		X					⁸ [X]	X		X	X	X							
CBC with differential	3	3		3	3		3		3				3		3	3	3							
Iron and serum ferritin	X						X						X											
Total bilirubin, AST, ALT, and ALP	4	4		4	4		4		4				4		4	4	4							
Creatinine	X	X		X									X											
⁵ HLA type														20										
HIV Ab/Ag Combo (other tests, if needed)	3																							

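### As written, 6.4.4 lets Week 18 samples from Group 2 subjects who never received dose 2 enter the post-second-dose response summary

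*Combined protocol and SAP*

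**What the plan says.** The secondary objective for Groups 2A-2D (3.2) is the antibody response to vaccine "administered as repeat dosing at 60 mcg IM via needle and syringe at two weeks after each injection". Section 6.2.2 attaches the second part of that objective to scheduled visits: "at Week 16 (Visit 07) and Week 18 (Visit 09) after the second vaccination".

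The main analysis rule in 6.4.4 is intent-to-treat: "all data from enrolled subjects will be analyzed according to the group assignment". Section 6.4.5 says that every sample on hand at a time point is used. The only stated exclusion from the main analysis is for subjects who are antibody-positive at baseline. An analysis by the vaccination scheme actually received is allowed, but as a secondary analysis and only where it is needed.

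Section 4.4.1 covers missed second doses: "subjects who do not receive the second injection as scheduled are expected to continue follow-up according to the Schedule of Evaluations for Group 1" subjects. The exception is that "research sample collections will be discontinued for pregnant women or others in which it is contraindicated".

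**The concern.** A subject who never receives dose 2 has no time point two weeks after a second injection. If that subject is still bled at Week 18, the sample measures a single 60 mcg dose 18 weeks later. Placing it in the Groups 2A-2D Visit 09 summary makes that summary answer a different question from the one in 3.2. If dose 2 raises the response, the reported two-dose response is too low.

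Intent-to-treat protects nothing here that would offset this. The study is open-label, the group is known before enrollment (4.2.3), and the Group 2 strata are defined by age, so there is no randomised comparison to preserve. Section 6.4.6 also lets results by group go to the sponsor before follow-up ends, to inform future trials, so the headline Week 18 figure may be used early.

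**Working it through.** **Step 1: do the samples exist?** Visit 09 in the Group 1 table of Appendix I is Week 18, Day 126. The daily blood volume is 56 mL, and the cumulative total rises from 719 to 775 mL (775 − 719 = 56). That equals 16 mL serum plus 40 mL PBMC and plasma. So a Group 2 subject moved to this schedule is bled at Week 18 unless sampling is contraindicated. Visits 11, 12 and 13 (Weeks 28, 40 and 52) are also common to both schedules and carry research draws.

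**Step 2: does a rule keep them out?** Sections 6.4.4 and 6.4.5 together put them in, by assigned group and by available sample. No sentence limits the Visit 09 summary to dose-2 recipients.

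**Step 3: the plan's own intervals.** Table 6-2, which 6.3.2 applies to response rates, gives 0.516-0.979 for 10/12. The Clopper-Pearson limits are the 0.025 quantile of Beta(10, 3) and the 0.975 quantile of Beta(11, 2), which reproduce 0.516 and 0.979. For x = n the lower limit is 0.025^(1/n): 0.735 for 12/12, as printed, and 0.692 for 10/10.

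**Step 4: size of the shift.** Let m be the number of sampled subjects without dose 2 in a group of 12, p2 the response rate after two doses, and p1 the Week 18 rate after one dose.

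Expected by-assignment rate = ((12 − m) × p2 + m × p1) / 12

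Shift = (m/12) × (p2 − p1)

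The shift is largest when p2 − p1 = 1: 1/12 = 8.3 points per subject in one age group, or 1/48 = 2.1 points in the four groups combined. If fewer than 12 subjects contribute, the actual number replaces 12.

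The documents give no value for m, p1 or p2, so the following are assumptions:

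| p2 | p1 | m = 1 | m = 2 | m = 3 |
|---|---|---|---|---|
| 0.9 | 0.5 | 0.867 | 0.833 | 0.800 |
| 0.9 | 0.1 | 0.833 | 0.767 | 0.700 |
| 0.6 | 0.5 | 0.592 | 0.583 | 0.575 |

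For example, (10 × 0.9 + 2 × 0.5)/12 = 10/12 = 0.833, against 0.90 in dose-2 recipients.

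**Step 5: the extreme case.** If every recipient responds and no non-recipient does:

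| m | By assignment | Dose-2 recipients only |
|---|---|---|
| 1 | 11/12 (0.615-0.998) | 11/11 (0.715-1) |
| 2 | 10/12 (0.516-0.979) | 10/10 (0.692-1) |
| 3 | 9/12 (0.428-0.945) | 9/9 (0.664-1) |

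**Step 6: titers.** If recipients' Week 18 titers are four times those of non-recipients (an assumption), the group geometric mean is multiplied by 4^(−m/12): 0.891, 0.794 and 0.707 for m = 1, 2 and 3.

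**The case against.** The best reply is that 6.4.4 already provides an analysis by actual vaccination scheme, and a one-dose Group 2 subject is plainly a case where actual and assigned schemes differ. That stands in part: the two-dose result can be produced. But it is conditional and secondary, and the plan does not say where a single-dose 60 mcg subject would go. Table 1 has no such group, since its only single-dose group receives 20 mcg.

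A second reply is that intent-to-treat fixes the group and does not relabel the time point. Section 6.2.2 speaks of samples after the second vaccination, and Group 1 visits are timed from Day 0 while the later Group 2 visits are timed from Visit 07. On that reading a non-recipient has no endpoint sample. This ambiguity is real. A reader might infer that the plan expressly counts these samples as two weeks after dose 2; it does not. It only fails to keep them out, while its general rules bring them in.

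Third, the effect may be small. With p2 = 0.6 and p1 = 0.5 the loss is 0.8 to 2.5 points for one to three subjects, against an interval about 46 points wide at 10/12. Section 6.4.5 expects missing data to be rare, although the samples at issue here are present, not missing. Not every non-recipient enters either: those in whom sampling is contraindicated, including pregnant women, and those who leave the study give no Week 18 sample.

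Finally, by-assignment analysis is legitimate for a treatment-policy question. That is true, but it is not the question in 3.2.

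**Conclusion.** The mismatch holds as a gap in the main analysis rule: read together, 4.4.1, 6.2.2, 6.4.4, 6.4.5 and Appendix I allow one-dose samples into the Week 18 post-second-dose summary. The possible loss is bounded at 8.3 points per sampled non-recipient in a group of 12. Whether any loss occurs depends on at least one sampled subject missing dose 2 and on p2 exceeding p1, and the documents settle neither.

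Three stronger readings are not supported. The contrast of 10/12 with 10/10 is a limiting case, not a forecast. Nothing in the documents shows that missed second doses will differ by age group. The main immunogenicity result is not compromised either: 1.6 sets its primary time point at two weeks after the first vaccination, before dose 2 is due. The Week 18 rates are descriptive, and 6.3.3 already calls the comparisons between age groups exploratory and unpowered. The point merits a wording change before analysis; no printed figure in the plan is wrong on this account.

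**What to change.** In 6.4.4, state that the main analysis for Week 18 and later post-dose-2 time points uses subjects who received dose 2. Report samples from Group 2 subjects without dose 2 separately, as single-dose 60 mcg data at the actual time since injection. Keep the by-assignment analysis as supportive. In each group, report how many second doses were missed and why.

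This is SAP wording only: no visit, sample or procedure changes, and no data are discarded. It has two costs. Denominators at Week 18 and later become slightly smaller. Conditioning on receipt of dose 2 also selects on events after baseline, since the reasons in 4.4.1 include related adverse events and intercurrent illness. The supportive analysis and the table of reasons let a reader judge that selection.
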